6.3 Concomitant treatments and medications (permitted and prohibited)

Any medication used, in addition to appearing in the clinical note, must be recorded in the concomitant medications section of the eCRF .

Permitted medications:

- Ophthalmic:

All permitted medications administered ophthalmically during the study must wait a minimum of 10 minutes after the last application of the study or reference treatments. This is to avoid treatment interactions with the tear film, based on the physiological tear flow rate and volume. [24]

- Tetracaine 0.5%
- Tropicamide 0.8% / Phenylephrine 5%
- Hypromellose 2%
- Fluorescein
- Lissamine green

- Systemic or other routes of administration other than ophthalmic:

- Any hormonal contraceptive will be included, including tablets, injections, and drug-releasing devices.

Prohibited medications:

- Any medication with ophthalmic application that is not on the list of permitted medications
- Any systemic medication that is not on the list of permitted medications.

6.4 Procedure for monitoring and measuring adherence

For over four decades, numerous investigations have been conducted on the appropriate way to measure and quantify medication adherence, however, none has reached a consensus to establish itself as the gold standard, both in cross-sectional and longitudinal studies. [25, 26, 27, 28, 29, 30, 31, 32]

There are different procedures for measuring adherence to pharmacological interventions. The most common procedure involves self-reports, which include patient interviews, questionnaires, and self-monitoring diaries. Their strengths are speed, flexibility, low cost, and ease of implementation; they have a high degree of specificity for nonadherence; however, their sensitivity and reliability for adherence are low. [32, 33]

Biochemical measurement of the drug, or its metabolite, is one of the methods that best confirms drug use. However, in addition to being costly and impractical, it is of little use in ophthalmic applications, as peripheral concentrations may be undetectable; and samples from other tissues require more invasive methods that would not be advisable. [32]

Medication counting is another way to measure adherence. Classically referred to as "pill counting," in ophthalmology it is translated as the weight of the bottle. This is a simple, inexpensive, and noninvasive method. The main disadvantages of this method are: 1. It cannot confirm the application of the medication (it could have been intentionally dropped or instilled outside the eye), and 2. It depends on the subject bringing the medication back. [32, 33]

Adhesion assessment will be based on the bottle's weight and will be performed taking into account the following information: drop weight, initial container weight, final container weight, and the total number of applications. The following simplified formula will be used:

$$Ad = \frac{(P_i - P_f)100}{P_T}$$

Where:

Ad = adhesion

P_i = weight of the container delivered to the subject at the beginning

P_f = weight of the container returned by the subject

P_T = weight of the dosage indicated for the investigational products

$$P_T = (P_g) G$$

Where:

P_g = weight of one drop of the medicine, determined by the research and development department

G = number of applications indicated for the investigational products

Containers that do not maintain their physical integrity will not be considered for the adherence calculation. Subjects who do not return the investigational product container by Visit 2 will be considered non-compliant.

There is no standardized parameter to define adequate adherence; this must be defined and outlined by the objectives of the particular research. [32]

For this study, a minimum adherence of 80% (by weight and diary) will be considered necessary to meet the research objectives. Therefore, subjects with less than 80% adherence will be included in the intention-to-treat population.

6.5 Strategies to improve adherence

1. The PI will educate the subject on the importance of correctly administering concomitant treatment to achieve the study objectives.
2. Direct questioning by the IP regarding the application of concomitant treatment.
3. Delivery of a printed calendar specifying the date of the visit and its activities.

If deemed necessary, text messages may be sent as reminders. The content of these messages must be approved in advance by the IEC.

7. Methods and procedures of the study

7.1 Research center

This study will be conducted at a research center previously evaluated by the sponsor. The center will be an institution or facility that conducts health research and complies with current regulations.

The research center will be responsible for forming a multidisciplinary research team to execute the clinical study according to the protocol. It is its prerogative to design the organization and select the personnel who will perform these functions. However, the sponsor requires that the PI and sub-investigator be physicians specializing in ophthalmology.

Any person assigned, under the PI's responsibility, to a part of the study monitoring (sub-investigator, nurse, etc.) or a specific role in the study (pharmacist, administrative assistant, study coordinator, etc.) must be listed in the "Delegation of Responsibilities."

The competency and training of all individuals directly involved in study activities must be verified prior to the conduct of any protocol-related activities. This must be recorded, and documents constituting evidence of this competency and/or training must be retained in the study master file. The competency and training of personnel involved in the study, both at the central level and at the study site, are the responsibility of the sponsor.

The sponsor must ensure that all study site personnel participating in the study are adequately trained in the study (research protocol, investigator's manual, amendments, standard operating procedures, etc.) and in ICH Good Clinical Practices prior to the start of their participation in the study. Training must be documented in writing and filed in the study master file.

7.2 Clinical study registration

This clinical study will be registered by the sponsor in public clinical trial registries prior to its initiation (inclusion of the first subject): the National Registry of Clinical Trials (RNEC) of the Federal Commission for the Protection against Sanitary Risks (COFEPRIS) and on a WHO primary registry platform. WHO primary registries meet specific criteria regarding content, quality and validity, accessibility, unique identification, technical capacity, and administration. WHO primary registries meet the requirements of the International Committee of Medical Journal Editors (ICMJE).

7.3 Treatment assignment

- This is an open-label, comparative study. All patients will receive the same treatment.

7.4 Outcome variables

7.4.1 Primary outcome variables

- Intraocular pressure.

- Heart rate.
- Systemic blood pressure.
- Pupillary diameter.
- Conjunctival hyperemia.

7.4.2 Secondary outcome variables

- Best corrected visual acuity (BCVA).
- Changes in ocular surface staining.
- Incidence of chemosis.
- Incidence of expected adverse events.
- Incidence of unexpected adverse events.

7.4.3 Exploratory variables

- Respiratory rate.
- Body temperature.

7.4.4 Definition of variables, methods and scales for their measurement

Table iii. Operational definition of variables

Variable	Conceptual Definition	Operational Definition	Type of measurement	Reference value	Statistical test
Intraocular Pressure	Tonometry is the objective measurement of IOP, based on the force required to flatten the cornea or the degree of corneal indentation produced by a fixed force.	By means of Goldmann tonometry based on the Imberk -Fick principle.	Discrete quantitative	10 – 21 mmHg	Wilcoxon one-sample signed-rank test
Heart rate	Pulse is a measurement of HR, that is, the number of times the heart beats per minute.	With each heartbeat, the left ventricle contracts and expels blood into the aorta. This forceful expulsion of blood creates a wave that is transmitted to the periphery of the body through the arteries.	Discrete quantitative	60 – 100 bpm	Wilcoxon one-sample signed-rank test

Variable	Conceptual Definition	Operational Definition	Type of measurement	Reference value	Statistical test
		It is measured with an electronic blood pressure monitor or manually.			
Systemic blood pressure	It is the force exerted by blood against the walls of the arteries. SBP is the pressure inside the artery when the heart contracts and pumps blood through the body; while DBP is the pressure inside the artery when the heart is resting and filling with blood.	Measured with a blood pressure monitor and a stethoscope.	Discrete quantitative	SBP: 120 – 139 mmHg DBP: 80 – 89 mmHg	Wilcoxon one-sample signed-rank test
Pupillary diameter	The natural pupil of the human eye is usually approximately circular, for a given subject, the pattern of aberrations, diffraction, depth of field and retinal illumination depend on the pupil diameter, which in turn varies depending on the ambient lighting.	The pupillary diameter results from the balance between the pupillary sphincter muscle and the radial fibers of the iris, which have only autonomic innervation [33].	Continuous quantitative	2 – 6 mm	Wilcoxon one-sample signed-rank test
Conjunctival hyperemia	It is defined as the simplest reaction of the conjunctiva to a stimulus; a red	Direct observation. Classification using	Qualitative ordinal	Degrees: 0= Normal 1= Very mild 2= Mild	Binomial X²

Variable	Conceptual Definition	Operational Definition	Type of measurement	Reference value	Statistical test
	appearance is observed secondary to vasodilation of the vessels of the conjunctiva of variable intensity.	the Efron scale (see appendix 16.1)		3= Moderate 4= Severe	
Changes in the AVMC	Spatial visual acuity is the ability to distinguish separate elements of an object and identify them as a whole. It is quantified as the minimum angle of separation (located at the nodal point of the eye) between two objects that allows them to be perceived as separate objects.	Snellen chart	Continuous quantitative	0.6 to 2.0	Wilcoxon one-sample signed-rank test
Changes in ocular surface staining	Detection of epithelial defects in the cornea and conjunctiva.	Direct observation with a slit lamp will be graded according to the SICCA (see annex 16.2) [34].	Discrete quantitative	0 to 12	Wilcoxon one-sample signed-rank test
Incidence of Chemosis	It is conjunctival edema, the result of an inflammatory reaction. It is classified as present or absent.	The evaluator will use a narrow beam of light at 60° and measure whether the conjunctiva separates by $\geq 1/3$ of the entire eyelid opening or if it extends beyond the gray line.	Nominal qualitative	Present / Absent	Binomial χ^2

Variable	Conceptual Definition	Operational Definition	Type of measurement	Reference value	Statistical test
Incidence of AE	Any adverse medical event that occurs in a patient or clinical research subject who has been administered a pharmaceutical product and that does not necessarily have a causal relationship with this treatment [35].	All AEs will be reported (according to the protocol) and not only those in which the PI suspects a causal relationship with the treatments.	• Discrete quantitative • Nominal qualitative	• Incidence • Seriousness (gravity) • Causality	Binomial χ^2
Respiratory rate	The process involves inspiration and expiration, diffusion of oxygen from the pulmonary alveoli to the blood and carbon dioxide from the blood to the alveoli, and the transport of oxygen to body tissues and organs.	RR is the number of breaths a person takes per minute at rest.	Discrete quantitative	12 – 16 rpm	Wilcoxon one-sample signed-rank test
Body temperature	A clinical parameter that reflects the physiological state of the body. It is the balance between heat production and heat loss.	Degree of heat or cold, expressed in terms of a specific scale, using a thermometer.	Continuous quantitative	36.7 – 37.4°C	Wilcoxon one-sample signed-rank test

Abbreviations: BCVA, best-corrected visual acuity; AE, adverse event; HR, heart rate; RR, respiratory rate; PI, principal investigator; bpm, beats per minute; DBP, diastolic blood pressure; SBP, systolic blood pressure; IOP, intraocular pressure; rpm, breaths per minute; χ^2 , Chi-square.

7.4.5 Description of the variables, methods and scales for their measurement

7.4.5.1 Intraocular pressure

Tonometry is the objective measure of IOP, based primarily on the force required to flatten the cornea, or the degree of corneal depression produced by a fixed force. Goldman tonometry is based on the Imbert-Fick principle. [34]

Tonometry will be performed after instillation of topical anesthetic with fluorescein and the use of a cobalt blue filter (after assessing surface staining). Two readings will be taken, and the average will be recorded in the clinical record. The average will be recorded in the eCRF .

Management as AEs: IOP peaks ≥ 24 mmHg should be reported as AEs, as well as increases in intraocular pressure greater than 5 mmHg between evaluations before and after application of the investigational product (visits 1 and 2).

7.4.5.2 Heart rate

Heart rate is the number of times the heart's ventricles contract per unit of time, usually per minute. [36]Heart rate measurement will be performed by direct auscultation of the chest with a stethoscope. In the case of women, wrist pulse measurement may be permitted. However, the method chosen for the patient will be the same one used at all visits.

For heart rate measurement, the patient must be calm and at rest. They will be asked to rest for at least 20 minutes upon arrival at the clinic before the measurement, and when the measurement is to be performed after medication administration, they must also rest for 20 minutes.

For protocol purposes, rest is defined as a state in which the patient is not agitated due to unnecessary physical exertion. The patient should be seated for most of the rest period, but may get up to walk to the bathroom.

An increase or decrease in heart rate greater than 15 bpm between the pre- and post-treatment check-ups of visits 1 and 2 will be considered abnormal.

Management as AE: Patients with heart rate greater than 100 bpm or less than 60 bpm.

7.4.5.3 Systemic blood pressure

It is the force exerted by blood flow on the walls of the arteries. Blood pressure is measured with two measurements: systolic (measured when the heart beats, when the pressure is at its highest) and diastolic (measured between heartbeats, when the pressure is at its lowest). When reporting, the systolic is written first, followed by the diastolic.[37]

A calibrated aerobic or mercury sphygmomanometer and a stethoscope will be used for measurement. The measurement should be taken with the left arm and should be done while resting.

An increase or decrease in systolic blood pressure greater than 15 mmHg and in diastolic blood pressure greater than 10 mmHg will be considered abnormal, between the evaluations before and after the application of the investigational product at visits 1 and 2.

Management as AE: Patients with systolic blood pressure of 140 mmHg or more and diastolic blood pressure of 90 mmHg or more.

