3.2 Hypothesis

H_0 = PRO-185 ophthalmic solution is safe and tolerable for ophthalmic use, as it occurred in 20% or less of subjects with any of the following adverse events: increased intraocular pressure (IOP >5 mmHg), heart rate variation (>15 bpm), increased systemic blood pressure [>15 mmHg systolic (SBP) or >10 mmHg diastolic (DBP)], pharmacological mydriasis, or grade 3 and 4 conjunctival hyperemia.

$$H_0: p - p_0 \leq \delta$$

H_1 = PRO-185 ophthalmic solution is not safe or tolerable for ophthalmic application because more than 20% of subjects experienced any of the following adverse events: increased IOP (>5 mmHg), heart rate variation (>15 bpm), increased systemic blood pressure [>15 mmHg systolic (SBP) or >10 mmHg diastolic (DBP)], pharmacological mydriasis, or grade 3 and 4 conjunctival hyperemia.

$$H_1: p - p_0 > \delta$$

Comparisons will be made between pre- and post-treatment measurements from visits 1 and 2, and between measurements from the baseline visit (before PT application) and measurements from the

final visit. Only one of the adverse event values described in the hypothesis need be abnormal with a frequency >20% between the comparisons (pre-treatment with post-treatment; or pre-PT baseline with values from the final visit) for the null hypothesis to be rejected.

4. Study design

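### Averaging of two readings is specified for IOP but not for heart rate or blood pressure, although all three are primary signs judged on fixed change limits; adding it is a cheap improvement whose size depends on repeatability and event wording that the documents do not settle

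*Protocol*

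**What the plan says.** Intraocular pressure, heart rate and systemic blood pressure are all primary outcome variables (Protocol 7.4.1).

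- **IOP (7.4.5.1):** "Two readings will be taken, and the average will be recorded in the clinical record". The average also goes to the eCRF.
- **Heart rate (7.4.5.2):** "Heart rate measurement will be performed by direct auscultation of the chest with a stethoscope". Wrist pulse is allowed for women, the method stays the same at all visits, and 20 minutes' rest is required. The limit is set by the sentence that begins "An increase or decrease in heart rate greater than 15 bpm between the pre- and post-treatment check-ups of visits 1 and 2 will be considered" and ends by calling such a change abnormal. No number of readings is given.
- **Blood pressure (7.4.5.3):** "The measurement should be taken with the left arm and should be done while resting". The device must be calibrated. No number of readings is given. The statement "Blood pressure is measured with two measurements: systolic (measured when the heart beats, when the pressure is at its highest) and diastolic" refers to the two components of one reading, not to a repeat.
- **SAP:** section 6, Table 2 and section 6.2 add no repeat or averaging rule.

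The blood-pressure limit is worded in two ways. The hypothesis in 3.2 counts "increased systemic blood pressure [>15 mmHg systolic (SBP) or >10 mmHg diastolic (DBP"), that is, increases only, joined by 'or'. Section 7.4.5.3 says "An increase or decrease in systolic blood pressure greater than 15 mmHg and in diastolic blood pressure greater than 10 mmHg will be considered abnormal": both directions, joined by 'and'.

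On the verdict, 3.2 says "Only one of the adverse event values described in the hypothesis need be abnormal with a frequency >20% between the comparisons" for the null hypothesis of safety to be rejected. The comparisons are pre/post at visit 1, pre/post at visit 2, and baseline against final visit.

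**The concern.** A change between two readings carries the error of both. When a change is cut at a fixed limit, reading error alone produces some events. Under the 3.2 wording a blood-pressure event also has two routes, systolic or diastolic. The trial is non-comparative, so no background rate can be subtracted.

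The protocol reduces this error for IOP and, without giving a reason, specifies no such step for two other primary signs under the same verdict rule. At stake is whether a 'not safe' result on blood pressure or heart rate could be told apart from reading noise. Repeat readings cannot be recovered at analysis.

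**Working it through.** **The plan's own figure.** Protocol 10.1.2 gives 18 subjects, raised to 22. With p0 = 0.20, margin 0.10, z = 1.96, power 0.80 and p = 0.10 (not given in the protocol's equation; inferred from the 10% incidence in SAP 4.1), and with the p(1 − p) variance of the SAP's formula:

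n = 0.10 × 0.90 × [(1.96 + 0.84)/(0.10 − 0.20 − 0.10)]² = 17.66, rounded up to 18; 18 × 1.2 = 21.6, so 22.

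With 22 subjects, 4 events are 18.2% and 5 are 22.7%, so the 20% line is crossed at 5.

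**Assumptions (not in the documents).** No drug effect; normal errors; within-subject SD of one reading s(SBP)/s(DBP) from 5/3.6 to 8/6 mmHg; SBP and DBP changes correlated 0.5.

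**Formulas.** SD of the change with single readings = s√2. With the mean of two readings whose errors correlate r within a sitting, SD of the change = s√(1 + r). Event under 3.2: P(ΔSBP > 15 or ΔDBP > 10). Event under 7.4.5.3 read literally: P(|ΔSBP| > 15 and |ΔDBP| > 10). Chance of crossing the line: P(X ≥ 5), X ~ Bin(22, p).

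**Worked case, SD 8/6, single readings.** The change SDs are 8√2 = 11.3 and 6√2 = 8.5. P(ΔSBP > 15) = 1 − Φ(1.33) = 9.2%. P(ΔDBP > 10) = 1 − Φ(1.18) = 11.9%. With correlation 0.5 both occur in 3.5%, so either occurs in 9.2 + 11.9 − 3.5, or 17.7% before rounding of the parts.

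| SD of one reading, SBP/DBP | 3.2 'or' rule: rate per comparison | P(5 or more of 22), one comparison | 7.4.5.3 'and' rule: rate per comparison |
|---|---|---|---|
| 5/3.6 | 3.8% | 0.1% | 0.7% |
| 6/4.5 | 8.5% | 3.5% | 2.3% |
| 7/5 | 12.3% | 13% | 4.1% |
| 8/6 | 17.7% | 35% | 7.1% |

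Under the 'and' rule the chance of 5 or more of 22 is 1.7% at 8/6 and 0.2% or less at the smaller SDs.

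**Where the expected rate passes 20%** ('or' rule, SBP:DBP SD ratio 1.4, comparisons independent). For a single comparison this needs about 8.8/6.3, above the range in the table. If a subject counts with an event at either visit 1 or visit 2, the rate is 1 − (1 − p)² and crosses 20% at about 6.6/4.7; at 7/5 it is 1 − 0.877² = 23%, and at 5/3.6 about 7%. Varying the SBP/DBP correlation from 0.3 to 0.7 moves the crossing only from 6.5/4.6 to 6.8/4.9. Pooling all three comparisons lowers it to about 5.9/4.2. Under the 'and' rule, two visits pooled cross at about 9.4/6.7.

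**Effect of averaging two readings at SD 8/6 ('or' rule, one comparison).**

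| Within-sitting correlation r | Event rate | P(5 or more of 22) |
|---|---|---|
| Single reading | 17.7% | 35% |
| 0 | 7.0% | 1.6% |
| 0.5 | 12.9% | 14% |
| 0.8 | 15.9% | 27% |

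**Heart rate**, limit 15 bpm either way: 2[1 − Φ(15/(s√2))]. At s = 5, 6 and 7 bpm the rate per comparison is 3.4%, 7.7% and 13.0%. At s = 7 the mean of two independent readings gives 2[1 − Φ(15/7)] = 3.2%.

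**The case against.** A reader might infer that reading noise alone will push the blood-pressure event above 20%. The documents do not support that. They give no repeatability figure for either sign. Within one comparison, every expected rate in the table is below 20%; what rises is the chance that a sample of 22 happens to reach 5. The 20% line is passed in expectation over this SD range only by pooling comparisons within a subject, which the plan does not clearly prescribe, and only at the larger SDs. Under the 'and' wording of 7.4.5.3 the problem nearly disappears. This objection stands and limits the claim.

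Nor does the protocol prescribe a single reading: it is silent on the number and does not forbid repeats. It already controls some variation through rest, a fixed arm, a calibrated device and a constant heart-rate method. These are reasons not to presume the larger SDs.

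The verdict rule is also less settled than the 20% sentence suggests. Sections 3.2 and 10.1.2 also state a margin of 0.10, and 10.3.1 sets alpha at 0.05. An exact one-sided 0.05 test with 22 subjects would need 9 events against 20%, or 11 against 30%, which noise at 12.3% would almost never reach (below 0.1% for 9). In the other direction, the SAP hypothesis (3.2) uses 10%, which noise would cross more easily.

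Finally, averaging is not a cure. It does not remove true drift over the 20-40 minutes after dosing or day-to-day change between baseline and final visit, and the gain shrinks when readings in one sitting share error. If individual values are kept for the absolute adverse-event limits, repeats add chances to cross them. These points reduce the benefit but do not reverse it: against the change limits, the mean of two readings has no larger error than one.

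**Conclusion.** The point holds as a cheap improvement, not as a demonstrated failure of the design. The omission is plain on the documents: averaging is specified for one primary sign and not for two others judged in the same way.

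Its consequence is conditional. With no drug effect, correlation 0.5 and the 3.2 wording, single readings imply a false blood-pressure event in about 4% to 18% of subjects per comparison over SDs of 5/3.6 to 8/6 mmHg, and a 0.1% to 35% chance of 5 or more of 22. With the 7.4.5.3 wording the rates are about 1% to 7%. No false-event rate can therefore be fixed until the two wordings are reconciled. The benefit of averaging at 8/6 lies between a fall from 18% to 7% (independent errors) and a fall from 18% to 16% (correlation 0.8).

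**What to change.** 1. In Protocol 7.4.5.2 and 7.4.5.3, require two readings 1-2 minutes apart at each scheduled time point and apply the change limits to their mean, as 7.4.5.1 does for IOP. Carry the rule into the SAP's variable definitions.
2. State whether the mean or the individual values apply to the absolute adverse-event limits in those sections, so that repeats do not add chances to cross them.
3. Reconcile the two wordings of the blood-pressure event (3.2 against 7.4.5.3: direction, and 'or' against 'and'), and state whether events are counted per comparison or pooled over visits.

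Cost: about 2 minutes per time point with the same staff and equipment. The schedule has seven such time points per subject, so about 14 minutes in all. The post-dose repeats must fit within the 20-40 minute window, which also holds the pupil, staining and IOP checks. If both values are entered, one extra eCRF field per sign is needed. No added visit or subject is required.
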